### **Treatment-related Adverse Event (TRAЕ)**

A treatment-related AE is any treatment-emergent AE with the relationship flag on the Events eCRF indicating there is a reasonable possibility that the event may have been caused by investigational medicinal product. In the unlikely event that the relationship is missing, the treatment-emergent event will be considered treatment-related and documented in a footnote of the treatment-related summary.

### **Disease-related Event**

Disease-related events are events (serious or non-serious) anticipated to occur in the study population due to the underlying disease. All serious disease-related events will be recorded and reported to the sponsor or designee within 24 hours. The investigator will submit any updated serious disease-related event data to the sponsor within 24 hours of it being available.

Disease-related events that would qualify as an adverse event or serious adverse event:

An event based on the underlying disease that is worse than expected as assessed by the investigator for the subject's condition or if the investigator believes there is a causal relationship between the investigational product(s)/study treatment/protocol-required therapies and disease worsening, this must be reported as an adverse event or serious adverse event.

Disease-related events that do not qualify as adverse events or serious adverse events:

An event which is part of the normal course of disease under study (e.g., disease progression in oncology or hospitalization due to disease progression) is to be reported as a disease-related event.

Disease-related events pre-defined for this study include: lupus-related joint pain, joint stiffness, joint swelling, rash, alopecia, and mucosal ulcers.

## **5.5 Demographic and Characteristics**

### **Age**

Age in years at randomization, which is collected in eCRF.

## **6. Analysis Sets**

### **6.1 Safety Analysis Set**

The safety analysis set will consist of all subjects who received at least 1 dose of investigational product. Safety analysis set will be used for analyses unless otherwise specified.

### **6.2 Pharmacokinetic Concentration Analysis Set**

The PK concentration analysis set will contain all subjects who have received AMG 592 and have at least one reported PK concentration.

### **6.3 Pharmacokinetic Parameter Analysis Set**

The PK parameter analysis set will consist of all subjects who have received AMG 592 and for whom at least one PK parameter can be adequately estimated.

### **6.4 Pharmacodynamic Analysis Sets**

The PD analysis set will consist of all subjects who have received AMG 592 or placebo, and for whom at least 1 PD parameters has a quantifiable baseline sample and at least one quantifiable post-baseline PD sample has been collected.

## **7. Planned Analyses**

### **7.1 DLRMs**

The study will have DLRMs for each cohort after the last subject in the cohort completes week 4 visit. Section 3.1 details the timings and scope of each DLRM planned for the study.

All available data the subjects up to and including the data snapshot date will be included in the analysis based on an “as-is” snapshot of the database without data locking. Data will be subject to ongoing checks for integrity, completeness and accuracy in accordance with the Data Management Plan; however, there is no requirement to resolve outstanding data issues ahead of the DLRM snapshot. DLRM analysis will include subject-level listings and plots of available safety data (labs, and vitals) for each

---

cohort and the BLRM analysis if required. The recommendations for dose escalation/dose modifications will be based on the DLRMs.

## **7.2 Final Analysis**

The final analysis will be done after all subjects have completed the study (i.e., the safety follow-up visit). Final lock for the study will be performed at this point and the study will be unblinded. All outstanding data issues will be resolved ahead of the final lock. All study data will be included in the clean snapshot of the database after the final data lock. All analyses described in this analysis plan will be performed as part of final analysis. Results from these analyses will be included in the Clinical Study Report.

## **8. Data Screening and Acceptance**

### **8.1 General Principles**

The objective of the data screening is to assess the quantity, quality, and statistical characteristics of the data relative to the requirements of the planned analyses.

### **8.2 Data Handling and Electronic Transfer of Data**

The Amgen Global Study Operations-Data Management (GSO-DM) department will provide all data to be used in the planned analyses. This study will use the RAVE database.

### **8.3 Handling of Missing and Incomplete Data**

All endpoints in the study will be analyzed as-is and no imputation is planned.

### **8.4 Detection of Bias**

Important protocol deviations and early withdrawal from treatment and from study may bias the results of the study. The incidence of these factors will be assessed and reason for early withdrawals will be tabulated.

### **8.5 Outliers**

Outlier data will not be excluded unless scientifically justified.

Pharmacokinetic (PK) serum concentration data will be evaluated for outliers by visual inspection, and decisions to re-assay individual samples will be made in accordance with standard pharmacokinetic evaluation practice.

### **8.6 Distributional Characteristics**

Not applicable for this study.

## **8.7 Validation of Statistical Analyses**

Programs will be developed and maintained and output will be verified in accordance with current risk-based quality control procedures.

Tables, figures, and listings will be produced with validated standard macro programs where standard macros can produce the specified outputs.

The production environment for statistical analyses consists of Amgen-supported versions of statistical analysis software; for example, the SAS System version 9.4 or later.

## **9. Statistical Methods of Analysis**

### **9.1 General Considerations**

Descriptive statistics will be provided for selected demographics, safety, PK, PD, immunogenicity, efficacy, and biomarker data. Descriptive statistics on continuous measurements will include means, medians, Q1, Q3, standard deviations, standard errors and ranges, while categorical data will be summarized using frequency counts and percentages. Data will be presented and summarized by treatment and also by time as appropriate.

For the DLRM analyses safety data will be listed and figures may be provided. The scope of review includes all available study data including demographics, medical history, concomitant therapies, adverse events, electrocardiograms, vital signs, laboratory results, and emerging pharmacokinetic and pharmacodynamics data.

### **9.2 Subject Accountability**

The number and percent of subjects who were enrolled, received at least one dose of investigational product, completed investigational product, discontinued from investigational product (including reasons for discontinuing), completed study, discontinued the study (including reasons for discontinuing) will be summarized overall and by dose cohort.

Key study dates for the first subject enrolled, last subject enrolled, and last subject's end of study will be presented.

A summary of number of subjects in each analysis subset will be provided.

### **9.3 Important Protocol Deviations**

Important protocol deviations (IPDs) categories are defined by the study team before the first subject's initial visit and updated during the IPD reviews throughout the study prior to database lock. These definitions of IPD categories, subcategory codes, and

descriptions will be used during the course of the study. The final IPD list is used to produce the Summary of IPDs table and the List of Subjects with IPDs.

Eligibility deviations are defined in the protocol. A list of deviations from eligibility criteria will also be generated.

The number of subjects with important protocol deviations and protocol deviations due to COVID-19 will be summarized in a table. A list of important protocol deviations and protocol deviations for subjects impacted by COVID-19 will also be provided.

## **9.4 Demographic and Baseline Characteristics**

### **9.4.1 Demographic**

- Age (years) at enrollment (continuous summary statistics)
- Age in categories (number and percentage of 18 – 64, 65 – 74, 75 – 84, ≥ 85 years)
- Sex (number and percentage of males and females)
- Ethnicity (number and percentage of Hispanic or Latino and Not Hispanic or Latino)
- Race (number and percentage of subjects in each race, or mixed-race combination)

### **9.4.2 Baseline Characteristics**

- Height, weight and Body Mass Index (BMI) (continuous summary statistics)
- Baseline SLEDAI-2K score (number and percentage of 0 to 5, 6 to 9, ≥ 10)
- Subject incidence (number and percentage) of baseline corticosteroids and baseline SLE-related medication

## **9.5 Efficacy Analyses**

### **9.5.1 Analyses of Exploratory Efficacy Endpoint (s)**

The SLEDAI-2K total score and change from baseline will be provided at all time points collected.

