^g Can be done as a part of the clinical chemistry

^h Pharmacokinetic and lymphocyte subset blood samples should be collected at the exact nominal time point as noted above (see hour postdose column). If unable to collect a blood sample at the specified nominal time point, collect it as close as possible to the nominal time point and record the actual collection time. For samples without exact nominal time point (ie, days 8 to 78), PK samples must be collected prior to administration of investigational product, where appropriate. Pharmacokinetic and lymphocyte subset samples not collected at exact nominal time point will not be considered protocol deviations.

ⁱ DNA will be extracted only in subjects who provide additional consent for pharmacogenetics testing.

^j Investigational product must be administered within \pm 12 hours from the scheduled time point up until week 4. After week 4, investigational product must be administered within \pm 1 day of the scheduled time point. If that window is missed, that dose will not be administered, and the next dose will be administered at the next scheduled dosing date. Subjects will remain at the site for at least 1 hour following the first and second doses of investigational product and for at least 30 minutes following subsequent doses.

^k Subjects who withdraw from investigational product early will complete an early termination visit that includes the week 12 (predose) assessments.

^l To be collected at screening but not required for eligibility unless subject has no documented prior history of antinuclear antibody (ANA) \geq 1:80 or elevated anti-dsDNA.

^m For description of home healthcare services available, see [Section 9.2.3.4](#).

Table 2-2. Schedule of Activities Follow-up

	Follow-up			
	13	14	16	18/SFU/EOS ^a
Study week				
Study day	92	99	113	127
GENERAL AND SAFETY ASSESSMENTS				
Weight				X
Vital signs	X	X	X	X
ECG				X
Adverse events	X	X	X	X ^a
Serious adverse events	X	X	X	X ^a
Disease-related events	X	X	X	X ^a
Concomitant medications review	X	X	X	X ^a
LABORATORY ASSESSMENTS				
Urine pregnancy test			X	X
Anti-dsDNA and C3 and C4 complement				X
Hematology		X	X	X
Chemistry				X
PBMC				X
PHARMACODYNAMIC ASSESSMENTS				
Lymphocyte subsets	X	X	X	X
PHARMACOKINETICS AND ANTIBODIES				
Pharmacokinetic samples	X	X	X	X
Anti-AMG 592 antibody				X
BIOMARKER				
Biomarker development sample				X

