7.8.2.1 SLE Therapies

Subjects who were receiving treatment with systemic SLE therapies must maintain a stable dose and the same route of administration through the end of study. No new systemic SLE therapies may be initiated during the study.

Approved

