7.8.2.2 Corticosteroids

For subjects entering the study while taking oral steroids, no dose adjustments are allowed for 12 weeks. After week 12 new corticosteroids administered by any route may be added or dose adjusted per investigator judgement.

8. Discontinuation Criteria

Subjects have the right to withdraw from investigational product and/or other protocol-required therapies, protocol procedures, or the study as a whole at any time and for any reason without prejudice to their future medical care by the physician or at the institution.

The investigator and/or sponsor can decide to withdraw a subject(s) from investigational product, device, and/or other protocol-required therapies, protocol procedures, or the study as a whole at any time prior to study completion for the reasons listed in [Sections 8.1, 8.2.1, and 8.2.2](#).

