8.1 Discontinuation of Study Treatment

Subjects (or a legally acceptable representative) can decline to continue receiving investigational product and/or other protocol-required therapies or procedures at any time during the study but continue participation in the study. If this occurs, the investigator is to discuss with the subject the appropriate processes for discontinuation from investigational product or other protocol-required therapies and must discuss with the subject the possibilities for continuation of the Schedule of Activities (see [Table 2-1](#), [Table 2-2](#)) including different options of follow-up (eg, in person, by phone/mail, through family/friends, in correspondence/communication with other treating physicians, from the review of medical records) and collection of data, including endpoints, adverse events, disease-related events, and must document this decision in the subject's medical records. Subjects who have discontinued investigational product and/or other protocol-required therapies or procedures should not be automatically removed from the study. Whenever safe and feasible, it is imperative that subjects remain on-study to ensure safety surveillance and/or collection of outcome data.

Subjects may be eligible for continued treatment with Amgen investigational product(s) and/or other protocol-required therapies by a separate protocol or as provided for by the local country's regulatory mechanism, based on parameters consistent with [Appendix 3](#).

Reasons for removal from protocol-required investigational product(s) or procedural assessments include any of the following:

- Decision by Sponsor
- Lost to follow-up
- Death
- Ineligibility determined
- Protocol deviation
- Non-compliance
- Adverse event
- Subject request
- Disease flare requiring treatment not allowed in the protocol (eg, colitis, asthma)

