## Appendix B. Analytical Windows

The last measurement for the endpoint of interest taken prior to or on the first dose of investigational product in this study, unless stated otherwise will be defined as a baseline visit and the analysis visit name will be “Baseline”. For any visit up to Day 1 pre-dose which is not a baseline visit, the analysis visit will be ‘Pre-Analysis’.

For post-dose assessments on Day 1, post-dose assessments on Day 85 (the day corresponding to week 12 dosing) and assessments at Safety follow-up/EOS visit, the analysis visit will be same as the scheduled visit.

Remaining visits (scheduled or unscheduled) after Day 1 for any assessment will be mapped to the analysis visit based on visit windows defined in the tables below for that assessment. Only visits applicable for that assessment will be considered for analysis.

Data collected through central lab and local lab will both be mapped into analysis visit windows. The local lab data can only be used in analysis when there are no central lab data available in the analysis visit window.

If more than one visit with non-missing data falls within an analysis visit window, the visit closest to the target day will be considered for analysis. If two visits are equidistant from the target day, the latest visit (or time if on the same day) will be considered. If more than one evaluation has same date and time (for chemistry, hematology or pharmacodynamics results), the value with the smallest accession number will be considered.

Analysis visit windows for selected assessments are included in tables below. For remaining assessments, no visit window will be applied. ‘Day 85’ used in study day window calculation in the tables below is the actual study day when Week 12 dose was received. If that dose is missing, then target Day 85 is used for the calculation.

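### The early-termination SLEDAI-2K and serology results have no analysis visit of their own, so some reach no summary and the Week 12 row covers only subjects assessed from Day 72

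*SAP*

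**What the plan says.** SAP 9.5.1 states: "The SLEDAI-2K total score and change from baseline will be provided at all time points collected". SAP 9.7.2 plans by-visit summaries of anti-dsDNA, C3 and C4 in the same way. On missing data, SAP 8.3 states: "All endpoints in the study will be analyzed as-is and no imputation is planned".

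Protocol 8.1 lists among the reasons for removal from product: "Disease flare requiring treatment not allowed in the protocol (eg, colitis, asthma". Sections 7.8.2.1 and 7.8.2.2 restrict lupus treatment during the study: "No new systemic SLE therapies may be initiated during the study" and "For subjects entering the study while taking oral steroids, no dose adjustments are allowed for 12 weeks". Section 7.1.7 also excludes non-oral corticosteroids.

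For those who stop, Protocol Table 2-1, footnote k, states: "Subjects who withdraw from investigational product early will complete an early termination visit that includes the week 12 (predose) assessments". Those assessments include SLEDAI-2K, anti-dsDNA, C3 and C4. The later safety follow-up visit for early terminators includes none of them.

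SAP Appendix B exempts from windowing only the baseline and pre-dose records, the post-dose assessments on Days 1 and 85, and the safety follow-up/end-of-study visit. For everything else: "Remaining visits (scheduled or unscheduled) after Day 1 for any assessment will be mapped to the analysis visit based on visit windows defined". When two visits fall in one window, "the visit closest to the target day will be considered for analysis".

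**The concern.** The ET visit is not among the exemptions, so its result competes with the scheduled visit in the same window. A subject who attended Day 29 and stopped on, say, Day 38 has two SLEDAI-2K scores in the Week 4 window. The Day 29 score is nearer the target, and the ET score appears in no summary although it was collected. If the subject leaves after the ET visit, nothing represents that subject at Week 12.

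This matters more for disease activity than for most measures because the outcome can itself cause the withdrawal. A flare that leads to removal yields a high score at the ET visit, and that is the score the selection rule may pass over. Planned groups are small: 5 AMG 592 and 2 placebo subjects in each of cohorts 1-3, and 3 and 1 in cohorts 4-5. One such subject is 20% (1/5) or 33% (1/3) of an AMG 592 group. In cohorts 4-5 it could be the only placebo subject.

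**Working it through.** The plan gives no figure for this point: no flare rate, withdrawal rate, SLEDAI-2K standard deviation or assumed effect. The check therefore traces the ET record through the SAP's own rules.

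**Inputs (SAP Appendix B).** SLEDAI-2K windows: Days 2-43 (target 29), 44-71 (target 57), 72 to 'Day 85' (target 85). Anti-dsDNA and C3/C4 windows: Days 2-15 (target 8), 16-43 (29), 44-71 (57), 72 to 'Day 85' (85). When the Week 12 dose is not given, 'Day 85' is target Day 85.

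**Assumptions.** Scheduled visits fall on target, and possible ET days run from 2 to 84, which is 83 days.

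**Step 1. The subject leaves the schedule after the ET visit.**

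| ET day | Days | SLEDAI-2K score appears under |
|---|---|---|
| 2-29 | 28 | Week 4 |
| 30-43 | 14 | nothing (Day 29 is closer) |
| 44-57 | 14 | Week 8 |
| 58-71 | 14 | nothing (Day 57 is closer) |
| 72-84 | 13 | Week 12 |

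- In no summary: 14 + 14 = 28; 28/83 = 34%.
- Under Week 4 or Week 8: 28 + 14 = 42; 42/83 = 51%.
- In the Week 12 row: 13/83 = 16%.

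For anti-dsDNA and C3/C4, Days 9-15 are also lost to the Day 8 visit: 7 + 14 + 14 = 35; 35/83 = 42%. Another 7 + 14 + 14 = 35 days appear under Day 8, Week 4 or Week 8, and 13 reach Week 12.

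If a scheduled visit is one day off target, each loss range shortens by one day. For SLEDAI-2K the count becomes at least 13 + 13 = 26.

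**Step 2. The subject stops product but keeps attending.** A scheduled score displaces the ET score on 41 days in the Week 4 window, 27 in the Week 8 window and 13 in the Week 12 window: 81 of 83. The Day 85 score then enters Week 12, so the subject is represented there, although the ET score itself is not shown.

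**Step 3. Direction.** Let d be the share of an arm missing from Week 12 because of flare, and g the mean change in those subjects minus the mean change in the rest (positive when they are worse).

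- Within-arm distortion of mean change = -d × g.
- Distortion of AMG 592 minus placebo = g × (d_placebo - d_AMG592).

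Illustration only; d and g are assumed:

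- Within arm, d = 10% and g = 4 to 8 points: -0.4 to -0.8 points.
- Contrast, g = 6: 0 with 10% lost in each arm; 6 × (0.25 - 0.10) = +0.9, against AMG 592, with 25% lost on placebo and 10% on AMG 592; -0.9, in favour of AMG 592, with those shares reversed.
- One cohort, remaining subjects at -4 and one flare subject at +4: Week 12 shows -4.0. With that subject included it would be (4 × -4 + 4)/5 = -2.4 for n = 5, or (2 × -4 + 4)/3 = -1.3 for n = 3.

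**The case against.** A reader might infer that Week 12 is a completers' analysis biased towards AMG 592. The documents do not support that.

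- **Not a completers' analysis.** Protocol 8.1 says that stopping product should not automatically end participation, and it presses for subjects to stay on study where safe and feasible. Those who stay can supply a Day 85 score, and ET scores from Day 72 count in any case. This stands. It does not bring back the flare score, and a later score may reflect treatment given after removal.
- **No fixed direction.** Step 3 shows that the between-arm distortion can be zero or run against AMG 592. This stands in full.
- **Most scores are still summarised.** For subjects who leave, about half of the possible ET days appear under Week 4 or Week 8. Nothing is deleted either: SAP 7.2 keeps all study data in the final database. The gap is in the summaries.
- **The flare clause is not specific to lupus.** Its examples are colitis and asthma. Protocol 7.1.7, 7.8.2.1 and 7.8.2.2 make removal for a lupus flare plausible, but that is inference.
- **Withdrawals are visible elsewhere.** SAP 8.4 acknowledges possible bias from early withdrawal, SAP 9.2 tabulates reasons for stopping, and SAP 9.6.2 tabulates disease-related events. None of these shows the ET score.
- **The plan names no end-of-treatment estimand.** The objective concerns various time points, and a by-visit row is correctly labelled as far as it goes. Even so, the selection rule conflicts with the undertaking to report every time point collected. SAP 9.7.1.2 has an explicit ET rule for pharmacodynamic data, while SLEDAI-2K and the serology have none.

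**Conclusion.** The point holds in a limited form. As written, the SAP leaves some collected ET results out of every summary, and its Week 12 row contains only subjects assessed from Day 72 to 'Day 85'. Where flare leads to removal and the subject then leaves the schedule, the within-arm Week 12 change can look better than it would with that subject included.

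The counts (28, 13 and 35 of 83) are shares of calendar days, not of subjects. They rest on scheduled visits falling on target. The actual loss is unknown, and at Week 12 it is little or none if subjects stay on schedule. The point sizes in Step 3 are assumptions and treat an ET score as if it were a Week 12 value. They may be generous, since Protocol 6.1 lists no minimum SLEDAI-2K and SAP 9.4.2 provides a baseline category of 0 to 5. A reader might infer from them a known bias in favour of the drug; they show only that one subject can matter in groups this small.

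SLEDAI-2K and the serology are exploratory and descriptive, and SAP 2.2 plans no formal hypothesis. The change is worth making because it is cheap and the data are already collected.

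**What to change.** In SAP 9.5.1, 9.7.2 and Appendix B, for SLEDAI-2K, anti-dsDNA, C3 and C4:

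- Add a supplementary row by treatment group: End of treatment (Week 12 pre-dose, or the ET visit for subjects who stopped early).
- Exempt the ET record from closest-to-target selection for that row only, and leave the existing by-visit rows unchanged.
- List each ET day and score.
- Show the number off product and the number who stopped for disease flare.

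The cost is SAP wording, one extra row in four descriptive tables and a short listing. No new data are needed and no clinical rule changes. The drawback is that the row mixes assessment days, so it should be labelled supplementary and read with the listing.
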